## 5.2 Investigational Study Drug Combination (THRIL)

### **Starting with Cycle 1:**

#### **A cycle is 28 days:**

Thalidomide 50 mg every ODD day, days 1-28 every 28 days

Lenalidomide every EVEN day, days 1-28 every 28 days at the dose indicated above and with possible dose escalation as described in 5.1.

Rituximab 375 mg/m^2 IV on days 1, 8, 15 and 22 (+/- 2 days) starting with Cycle 1 and then again on the same weekly x 4 schedule every 6th cycle through Cycle 19 (Cycles 7, 13, and 19).

Responses will be assessed at monthly intervals using the response criteria outlined by the IWCLL update of the 1996 NCI-Working Group criteria. Patients will remain on treatment until they demonstrate disease progression or unacceptable toxicity. It will be important for the investigator to differentiate disease progression from tumor flare. While no strict criteria can be established for this distinction, rapid changes in clinical status that occur within four weeks of a dose escalation are likely to be tumor flares and should be treated as such.

Tumor flare has been described with both thalidomide and lenalidomide treatment. Therefore, patients should be monitor closely for signs and symptoms of tumor flare for four weeks after each increase in dose. Prophylaxis for (TFR) is not recommended. Grade 1 TFR may be treated with NSAIDs (i.e. ibuprofen 400-600 mg orally every 4-6 hours as needed). TFR  $\geq$  Grade 2 may be treated with corticosteroids. Narcotic analgesics may be added as needed for pain control in subjects experiencing  $\geq$  Grade 2 tumor flare. If corticosteroids are used, the following dosage schedule is

recommended: prednisone 20 mg PO QD x 7 days followed by 10 mg PO QD x 7 days. (See Appendix D: Cairo Bishop Tumor Lysis Definition and Grading Criteria.)

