### 5.4 Drug Administration

#### 5.4.1 Dosing regimen

- Cycle -1: patients will receive thalidomide 50 mg PO daily on days 1-14 or lenalidomide PO on days 1-14, followed by no treatment days 15-28, as described previously in 5.1.
- Cycle 1 and subsequent cycles: Patients will receive thalidomide 50 mg (every **ODD** day on days 1-28 of a 28 day cycle) with lenalidomide (every **EVEN** day on days 1-28 of a 28 day cycle), as described previously. Each cycle will be 28 days in length.
- Cycle 1: Patients will also receive rituximab 375 mg/m^2 IV on Days 1, 8, 15 and 22 and then again on the same weekly x 4 schedule every 6th cycle through Cycle 19 (Cycle 7, 13, and 19), as described previously.

Patients unable to tolerate either thalidomide or lenalidomide will be removed from protocol. Patients unable to tolerate rituximab can continue on with protocol treatment without additional rituximab being administered.

Dosing of thalidomide and lenalidomide should be at bedtime in order to allow for the sedative effects of thalidomide to not cause daytime somnolence and to maintain regular dosing intervals. **Only enough lenalidomide for one cycle of therapy will be supplied to the patient each cycle.** At the start of any non-clinic visit treatment cycles subsequent to Cycle 24, one cycle of study drug will be shipped to the subject.

See Section 5.5 for allopurinol and oral hydration requirements as prophylaxis against tumor lysis syndrome (TLS).

Thalidomide and lenalidomide capsules should be swallowed whole, and should not be broken, chewed or opened.

If a dose of thalidomide or lenalidomide is missed, it should be taken as soon as possible on the same day. If it is missed for the entire day, it should not be made up.

Patients who take more than the prescribed dose of thalidomide or lenalidomide should be instructed to seek emergency medical care if needed and contact study staff immediately.

Subjects experiencing adverse events may need study treatment modifications (See section 5.6).

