
Non-blistering rash Grade 3
	
 
• If Grade 3, hold lenalidomide, thalidomide, and, if applicable, rituximab dosing. Omitted doses are not made up..
 
• Follow weekly.
 
• If rash development is related to a rituximab infusion, restart treatment as scheduled at the previous doses once toxicity resolves to <math>\leq</math> grade 1.
 
• If the development of the rash is not related to a rituximab infusion, and the rash is purpuric, vasculitic, or bullous, or possibly the result of Stevens-Johnson Syndrome or toxic epidermal necrolysis, the patient will be discontinued from the study.
 
• If the development of the rash is not related to a rituximab infusion and inconsistent with Stevens - Johnson syndrome, the clinician may re-institute therapy once the toxicity resolves to <math>\leq</math> grade 1. Re-institute lenalidomide monotherapy at a one dose level reduction. If no recurrence of the rash occurs after one week, then restart thalidomide monotherapy at 50 mg every other day. Further dose escalation of the lenalidomide will be at the discretion of the treating physician per guidelines in Section 6.2.
 

Grade 4
	
 
• Discontinue treatment and remove patient from study.
 

Desquamating (blistering) rash- any Grade
	
 
• Discontinue treatment and remove patient from study.
 

Neuropathy Grade 3
	
 
• Hold lenalidomide and, if applicable, rituximab, and discontinue thalidomide doses. Follow weekly. Omitted doses are not made up..
 
• When toxicity improves to <math>\leq</math> grade 2, restart treatment as scheduled. Restart lenalidomide one dose level lower. Thalidomide will not be re-introduced given its strong association with neuropathy.
 

Grade 4
	
 
• Discontinue lenalidomide. Remove patient from study.
 

Venous thrombosis/embolism <math>\geq</math> Grade 3
	
 
• Hold lenalidomide, thalidomide, and, if applicable, rituximab, doses and start anticoagulation; restart lenalidomide and thalidomide dosing at investigator's discretion (maintain dose level).
 
• Omitted doses are not made up..
 

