Serious dermatologic reactions including toxic epidermal necrolysis and Stevens-Johnson syndrome, which may be fatal, have been reported in association with thalidomide therapy. THALOMID® should be discontinued, if a skin rash occurs and only resumed following appropriate clinical evaluation. If the rash is purpuric, vasculitic, exfoliative, or bullous or if Stevens-Johnson syndrome or toxic epidermal necrolysis is suspected, use of THALOMID® should not be resumed.

The use in Thalidomide in Multiple Myeloma results in an increased risk of venous thromboembolic events, such as deep vein thrombosis and pulmonary embolus. The risk increases significantly when thalidomide is used in combination with standard chemotherapeutic agents including dexamethasone. In one controlled trial the rate of venous thromboembolic events was 22.5% in patients receiving thalidomide in combination with dexamethasone compared to 4.9% receiving dexamethasone alone. Patients and physicians are advised to be observant for signs of thromboembolism. Patients should seek medical attention should they develop symptoms such as shortness of breath, chest pain or leg or arm swelling. Preliminary reports suggest that patients who are appropriate candidates may benefit from concurrent prophylactic anticoagulation or aspirin treatment.

Although not reported from pre-marketing controlled clinical trials, seizures, including grand mal convulsions, have been reported during post-approval use of THALOMID® (thalidomide) in clinical practice. Because these events are reported voluntarily from a population of unknown size, estimates of frequency cannot be made. Most patients had disorders that may have predisposed them to seizure activity, and it is not currently known whether thalidomide has any epileptogenic influence. During therapy with thalidomide, patients with a history of seizures or with other risk factors for the development of seizures should be monitored closely for clinical changes that could precipitate acute seizure activity.

**THALOMID®(thalidomide) can cause severe birth defects in humans. Women and men taking thalidomide must take special precautions and be willing and able to comply with all aspects of the FDA-mandated S.T.E.P.S.® program. (see Appendix A: Risks of Fetal Exposure, Pregnancy Testing Guidelines and Acceptable Birth Control Methods).**

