#### 8.3.3 **Human Toxicology**

No dose-limiting effects were observed in the Phase I/II studies. Reported adverse events including fever, chills, headache, nausea, vomiting, rhinitis, asthenia, and hypotension, occurred primarily during rituximab infusions and typically responded to an interruption of the infusion and resumption at a slower rate.

**Fatal Infusion Reactions:** Severe and fatal cardiopulmonary events, including angioedema, hypoxia, pulmonary infiltrates, acute respiratory distress syndrome, myocardial infarction, and cardiogenic shock, have been reported. These severe reactions typically occurred during the first infusion with time to onset of 30-120 minutes.

**Cardiac Events:** Patients with preexisting cardiac conditions, including arrhythmia and angina, have had recurrences of these cardiac events during rituximab infusions.

**Tumor Lysis Syndrome:** Tumor lysis syndrome has been reported and is characterized in patients with a high number of circulating malignant cells ( $\geq 25,000/\text{mm}^3$ ) by rapid reduction in tumor volume, renal insufficiency, hyperkalemia, hypocalcemia, hyperuricemia, and hyperphosphatemia.

**Renal Events:** Rituximab has been associated with severe renal toxicity including acute renal failure requiring dialysis, and in some cases has led to death. Renal toxicity has occurred in patients with high numbers of circulating malignant cells ( $\geq 25,000/\text{mm}^3$ ) or high tumor burden who experience tumor lysis syndrome and in patients administered concomitant cisplatin.

**Mucocutaneous Reactions:** Severe bullous skin reactions, including fatal cases of toxic epidermal necrolysis and paraneoplastic pemphigus, have been reported in patients treated with rituximab. The onset of reaction has varied from 1 to 13 weeks following rituximab exposure.

**Hematologic Events:** In clinical trials, Grade 3 and 4 cytopenias were reported in 48% of patients treated with rituximab; these include: lymphopenia (40%), neutropenia (6%), leukopenia (4%), anemia (3%), and thrombocytopenia (2%). The median duration of lymphopenia was 14 days (range, 1 to 588 days) and of neutropenia was 13 days (range, 2 to 116 days). A single occurrence of transient aplastic anemia (pure red cell aplasia) and two occurrences of hemolytic anemia following Rituximab therapy were reported.

In addition, there have been a limited number of postmarketing reports of prolonged pancytopenia, marrow hypoplasia, and late onset neutropenia.

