Physicians should consider PML in any patient presenting with new onset neurologic manifestations. Consultation with a neurologist, brain MRI, and lumbar puncture should be considered as clinically indicated. In patients who develop PML, rituximab should be discontinued and reductions or discontinuation of any concomitant chemotherapy or immunosuppressive therapy should be considered.

**Bowel Obstruction and Perforation:** Abdominal pain, bowel obstruction and perforation, in some cases leading to death, were observed in patients receiving Rituxan in combination with chemotherapy for DLBCL. In post-marketing reports, which include both patients with low-grade or follicular NHL and DLBCL, the mean time to onset of symptoms was 6 days (range 1–77) in patients with documented gastro-intestinal perforation. Complaints of abdominal pain, especially early in the course of treatment, should prompt a thorough diagnostic evaluation and appropriate treatment.

**Additional Safety Signals:** The following serious adverse events have been reported to occur in patients following completion of rituximab infusions: arthritis, disorders of blood vessels (vasculitis, serum sickness and lupus-like syndrome), eye disorders (uveitis and optic neuritis), lung disorders including pleuritis and scarring of the lung (bronchiolitis obliterans), that may result in fatal outcomes, and fatal cardiac failure.

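### For a Grade 3 non-blistering rash tied to a rituximab infusion, Table 2 restarts thalidomide whatever the rash type, while Section 8.2.3 bars resumption after purpuric or vasculitic rash or suspected SJS/TEN

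*Combined protocol and SAP*

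**What the plan says.** Section 6.3, Table 2, has a row for Grade 3 non-blistering rash. Its first bullet holds lenalidomide, thalidomide and, if it is being given, rituximab. Three later bullets decide what happens next:

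- **Third bullet, rash related to a rituximab infusion:** "If rash development is related to a rituximab infusion, restart treatment as scheduled at the previous doses once toxicity resolves to" grade 1 or lower. The only conditions are attribution and grade.
- **Fourth bullet, rash with any other attribution:** "and the rash is purpuric, vasculitic, or bullous, or possibly the result of Stevens-Johnson Syndrome or toxic epidermal necrolysis, the patient will be discontinued". Such a patient leaves the study.
- **Fifth bullet, rash not related to an infusion and not consistent with SJS:** lenalidomide may return first, one dose level down, with thalidomide added after a week without recurrence.

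Grade 4 rash, and blistering or desquamating rash of any grade, each have an entry that stops treatment and removes the patient.

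Section 8.2.3, on thalidomide toxicology, sets a rule by type of eruption: "rash is purpuric, vasculitic, exfoliative, or bullous or if Stevens-Johnson syndrome or toxic epidermal necrolysis is suspected, use of THALOMID® should not be resumed". That sentence does not mention what caused the rash.

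**The concern.** For one group of rashes the protocol gives two instructions with opposite outcomes. An investigator who follows the third bullet restarts thalidomide at its previous dose. One who follows Section 8.2.3 does not give it again, and under Section 5.6 that ends protocol treatment.

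At stake is re-exposure to thalidomide after a type of rash for which the protocol's own safety text advises against resuming it, in a paragraph about skin reactions that may be fatal. Within Table 2, a purpuric or vasculitic rash leads to restart or to discontinuation purely according to whether it is judged related to an infusion.

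**Working it through.** No arithmetic applies. The check sets the instructions side by side and then looks for other text that would reconcile them.

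**Does the restart include thalidomide?** Yes. The third bullet restarts treatment at the previous doses, and the treatment held in the first bullet includes thalidomide. The bullet contains no discretionary wording, whereas the fifth bullet and the row for other non-hematologic toxicity both do.

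**Outcome by rash type, for a Grade 3 rash attributed to a rituximab infusion and resolved to grade 1 or lower:**

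| Rash type | Table 2 | Section 8.2.3 | Conflict? |
|---|---|---|---|
| Purpuric or vasculitic, not blistering | Restart thalidomide at previous dose | Do not resume | Yes |
| SJS/TEN suspected, no blistering yet | Restart thalidomide at previous dose | Do not resume | Yes, but rare |
| Bullous, blistering or desquamating | Removed by the blistering row | Do not resume | No |
| Any other rash | Restart at previous doses | May resume after clinical evaluation | No direct conflict |

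A Grade 4 rash is removed by its own entry and never reaches the restart bullet.

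**Does other text resolve it?**

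- Section 6.2 allows a new cycle once a drug-related rash is grade 1 or lower. It checks grade only, not type.
- Section 5.6 lets the investigator stop for an adverse event that may cause severe or permanent harm. That permits stopping but does not correct the instruction to restart.
- Section 5.4.1 says: "Patients unable to tolerate rituximab can continue on with protocol treatment without additional rituximab being administered". This concerns continuing without rituximab and does not say whether thalidomide is safe to resume.

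**Is Section 8.2.3 only background?** It is product information, but the fourth bullet of the Table 2 row turns nearly the same list of rash types into a mandatory stop. The protocol therefore already treats these types as decisive, and then limits the stop by attribution.

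**The case against.** The strongest reply is that the split by attribution is deliberate. Section 8.2.3 sits in the thalidomide part of the pharmaceutical information, and its paragraph opens with reactions reported in association with thalidomide. It can be read as covering only rash in which thalidomide is a suspect. Table 2 would then apply it properly by first asking whether an infusion was the cause, in line with Section 6.1, which holds the agent believed responsible. This reading is possible, but neither section states it. The authors may also have had ordinary infusion rash in mind for the third bullet, but that limit is not written either.

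Three stronger inferences are tempting, and the documents do not support them.

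- A reader might infer that the protocol restarts thalidomide after TEN or other blistering reactions. It does not, because the blistering and Grade 4 entries remove those patients whatever the cause.
- A reader might infer from Section 8.3.3 that infusions are known to cause the rashes in question. That section does report severe bullous reactions, "including fatal cases of toxic epidermal necrolysis and paraneoplastic pemphigus, have been reported in patients treated with rituximab", and lists "disorders of blood vessels (vasculitis, serum sickness and lupus-like syndrome") among its safety signals. But it gives the skin reactions an onset of 1 to 13 weeks after exposure and places vasculitis after infusions are completed. These are mostly bullous or delayed events, not infusion rashes. They show only that rituximab can be linked to such reactions. Whether a delayed one counts as related to an infusion is left undefined.
- A reader might infer from the schedule, with thalidomide every odd day and rituximab "on days 1, 8, 15 and 22 (+/- 2 days) starting with Cycle 1", that attribution will usually be wrong. The overlap measures no risk, and onset during an infusion is itself informative.

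It also stands that a careful investigator could use Section 5.6 to stop. That reduces the practical risk without making the two instructions agree.

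**Conclusion.** The inconsistency holds, in a narrow form. It covers a Grade 3 non-blistering rash that is purpuric or vasculitic or, rarely, one where SJS/TEN is suspected before blistering, when the rash is attributed to a rituximab infusion. For those patients Table 2 restarts thalidomide at the previous dose and Section 8.2.3 says not to resume it.

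The conclusion rests on two readings: that restarting treatment at previous doses includes every held drug, and that Section 8.2.3 applies whatever the cause, since it states no limit. It also takes exfoliative rash to be covered by the desquamating row.

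The documents give no frequency for these rashes, so no number of patients can be stated. The two-stage response rule, alpha, power and sample size are not affected. This is a specific safety wording problem in one table row. It is worth correcting because the rule as written points the wrong way against the protocol's own safety text.

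**What to change.** Change two bullets in the Grade 3 non-blistering rash row of Table 2:

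- **Third bullet:** allow restart at previous doses after an infusion-related rash only if the rash is neither purpuric nor vasculitic and SJS/TEN is not suspected.
- **Fourth bullet:** remove the attribution condition, so that its discontinuation rule applies whatever the cause.

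Other rashes attributed to an infusion keep the present restart at full dose. If the sponsor does intend rituximab attribution to override Section 8.2.3, the protocol should say so and give the reason.

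The cost is protocol wording in one row. The clinical downside is that a few patients with these rashes would leave treatment: Section 5.6 ends treatment when thalidomide is discontinued for any reason, although intolerance of rituximab alone does not.

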## Treatment Compliance

At all times, when dispensing protocol therapy, research center personnel will review the instructions, printed on the packaging, with subjects. Subjects will be asked to maintain a medication log to record the drug administration. Subjects will be asked to bring any unused drug and empty drug containers to the research center at their next visit. Research personnel will count and record the number of used and unused drug at each visit and reconcile with the patient medication log. Any unused Thalomid® (thalidomide) or Revlimid® (lenalidomide) should be returned to the patient for disposition in accordance with the STEPS® and RevAssist® programs. At the start of any non-clinic visit treatment cycles subsequent to Cycle 24, the packaging instructions will be reviewed with subjects by telephone call, and study drug and medication log will be shipped to the subject.

## 7. ADVERSE EVENT REPORTING REQUIREMENTS

Adverse event (AE) monitoring and reporting is a routine part of every clinical trial. The investigator will be required to provide appropriate information concerning any findings that suggest significant hazards, contraindications, side effects, or precautions pertinent to the safe use of the drug under investigation. Safety will be monitored by evaluation of adverse events reported by patients or observed by investigators or research staff, as well as by other investigations such as clinical laboratory tests, x-rays, electrocardiographs, etc.

### 7.1 Adverse Event Characteristics

- **CTCAE term (AE description) and grade:** The descriptions and grading scales found in the revised NCI Common Terminology Criteria for Adverse Events (CTCAE) version 4.0 will be utilized for AE reporting. A copy of the CTCAE version 4.0 can be downloaded from the CTEP web site (<http://ctep.cancer.gov>).
- **Attribution of the AE:**
  - Definite – The AE *is clearly related* to the study treatment.
  - Probable – The AE *is likely related* to the study treatment.
  - Possible – The AE *may be related* to the study treatment.
  - Unlikely – The AE *is doubtfully related* to the study treatment.
  - Unrelated – The AE *is clearly NOT related* to the study treatment.

### 7.2 Recording of Adverse Events

All adverse events will be recorded on a patient specific adverse event log. The AE log will be maintained by the research staff and kept in the patient's research chart.

### 7.3 Serious Adverse Event (SAE) Reporting

#### 7.3.1 Definition of SAE

##### Serious Adverse Event (SAE) Definition

A serious adverse event is one that at any dose (including overdose):

- Results in death
- Is life-threatening
- Requires inpatient hospitalization or prolongation of existing hospitalization
- Results in persistent or significant disability or incapacity
- Is a congenital anomaly or birth defect
- Is an important medical event
- Positively identified pregnancy

“Life-threatening” means that the subject was at immediate risk of death at the time of the serious adverse event; it does not refer to a serious adverse event that hypothetically might have caused death if it were more severe.

“Persistent or significant disability or incapacity” means that there is a substantial disruption of a person’s ability to carry out normal life functions.

Medical and scientific judgment should be exercised in deciding whether expedited reporting is appropriate in situations where none of the outcomes listed above occurred. Important medical events that may not be immediately life-threatening or result in death or hospitalization but may jeopardize the patient or may require intervention to prevent one of the other outcomes listed in the definition above should also usually be considered serious. Examples of such events include allergic bronchospasm requiring intensive treatment in an emergency room or at home, blood dyscrasias or convulsions that do not result in inpatient hospitalization, or the development of drug dependency or drug abuse. A new diagnosis of cancer during the course of a treatment should be considered as medically important.

